#### Analysis method to use if mixed-effects logistic models fail to reach convergence

If the analysis model for the primary analysis or any of the secondary analysis being analysed using mixed-effect logistics models fails to converge the following strategy will be employed:

|   | Change from previous strategy   | Example Stata code   |
|---|---|--|
| 0 | Primary analysis  | melogit postopinfec_30 i.treat /// i.plan_surg_proc i.asa_grade /// age_spline* haemoglobin_spline* /// creatinine_spline* gender   country: |
| 1 | Include country as a fixed-effect in place of random effect.  | logit postopinfec_30 i.treat /// i.plan_surg_proc i.asa_grade /// age_spline* haemoglobin_spline* /// creatinine_spline* gender i.country    |
| 2 | Remove the fixed-effect for country   | logit postopinfec_30 i.treat /// i.plan_surg_proc i.asa_grade /// age_spline* haemoglobin_spline* /// creatinine_spline* gender              |
| 3 | Adjust for age, creatinine and haemoglobin (if included in model) using a single continuous variable  | <pre>logit postopinfec_30 i.treat ///     i.plan_surg_proc i.asa_grade ///     age haemoglobin ///     creatinine gender</pre>               |
| 4 | Remove covariates in the following order. After each covariate is removed the model is run to see if convergence is reached: Gender, baseline haemoglobin, baseline creatinine, planned surgical procedure, age, ASA grade. | <pre>logit postopinfec_30 i.treat ///     i.plan_surg_proc i.asa_grade ///     age</pre>   |

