#### **Randomisation procedure**

Randomisation will occur after the patient has provided informed consent and shortly before the surgical procedure is due to start. Patients will be centrally allocated to treatment groups in a 1:1 ratio by minimisation with a random component. Minimisation variables will be country, surgical procedure category, and American Society of Anesthesiologists (ASA) grade. The surgical procedure categories are: i) resection of colon, rectum or small bowel; ii) resection of pancreas and bowel; iii) resection of stomach (non-obesity surgery); iv) resection of oesophagus (non-obesity surgery); v) obesity surgery; vi) other surgery involving gut resection. The ASA grades are: II, III, and IV. Each patient will be allocated with 80% probability to the group that minimises the between group differences in these factors among all patients recruited to the trial to date, and to the alternative group with 20% probability. To enter a patient into the OPTIMISE II trial, research staff at the site will log on to a secure web-based randomisation and data entry platform hosted by Queen Mary University of London and complete the patient's details to obtain a unique patient identification number and allocation to a treatment group. A patient's treatment group allocation will only be revealed to the person performing randomisation.

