#### **Analysis of primary outcome**

The primary outcome, postoperative infection within 30 days of randomisation, will be analysed using a mixed-effects logistic regression model with a random intercept for country (3), adjusting for planned surgical procedure, ASA grade, gender, age, baseline haemoglobin, and baseline creatinine. Planned surgical procedure and ASA grade will be included as the model as categorical variables. The categories for planned surgical procedure are i) resection of colon, rectum or small bowel; ii) resection of pancreas and bowel; iii) resection of stomach (non-obesity surgery); iv) resection of oesophagus (non-obesity surgery); v) obesity surgery; vi) other surgery involving gut resection. The categories for ASA grade are II, III, and IV. Age, baseline haemoglobin, and baseline creatinine will be modelled using using restricted cubic splines with three knots (with knot locations based on Harrell's recommendations: 10th percentile, 50th percentile and 90th percentile of covariate) (4, 5).

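### The non-convergence fallback discards country, a minimisation factor, before trying the nearly free step of making the splines linear

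*SAP*

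**What the plan says.** SAP section 4 (Randomisation procedure) states: "Minimisation variables will be country, surgical procedure category, and American Society of Anesthesiologists (ASA) grade". It adds that "Each patient will be allocated with 80% probability to the group that minimises the between group differences in these factors". Section 5 (Analysis of primary outcome) specifies a "mixed-effects logistic regression model with a random intercept for country", with three-knot restricted cubic splines for age, haemoglobin and creatinine.

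The fallback table in section 5 covers the primary outcome and the secondary outcomes that use a mixed logistic model: 180-day mortality, 30-day acute cardiac events and 30-day acute kidney injury. Its order is:

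1. "Include country as a fixed-effect in place of random effect"
2. "Remove the fixed-effect for country"
3. "Adjust for age, creatinine and haemoglobin (if included in model) using a single continuous variable"
4. Remove covariates one at a time, in the order "Gender, baseline haemoglobin, baseline creatinine, planned surgical procedure, age, ASA grade"

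No reason is given for this order.

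**The concern.** Minimisation balances the arms on country. If infection risk differs between countries, that balance reduces the sampling variation of the treatment estimate. A model with country in it reflects the reduction; a model without it does not. The standard error without country is therefore larger than the real variability of the estimate, and the test rejects less often than 5% under the null. As in any logistic model that omits a prognostic factor, the odds ratio also moves toward 1 and power falls.

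The table accepts this at step 2 while three sets of spline terms and gender remain in the model. The fallback is pre-specified, so once it is triggered the team is bound to give up a design factor before trying a simplification that costs almost nothing.

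**Working it through.** **Inputs from the SAP.** 1251 per arm (2502 in total), 30% vs 25%, 80% power, 5% type I error, two-sided p-values, minimisation with 80% probability on country, procedure (6 levels) and ASA grade (3 levels).

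**The plan's own figure.** With pooled variance and no continuity correction:

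n per arm = [1.960 × √(2 × 0.275 × 0.725) + 0.842 × √(0.30 × 0.70 + 0.25 × 0.75)]² / 0.05² = (1.238 + 0.531)² / 0.0025 ≈ 1251.

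This reproduces 2502. Power for 30% vs 24% comes to 92.3%, against the stated 92%. Neither figure depends on the fallback.

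**How likely step 2 is.** Expected primary events: 1251 × 0.30 + 1251 × 0.25 = 688. An ordinary logit with country indicators is unlikely to fail at that count. It is more likely to fail for acute kidney injury, where the SAP itself expects a lower event rate.

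**Effect of dropping country.** Each simulated trial had 2502 patients and 80/20 minimisation on the three factors. Control risk was 30% and the treatment odds ratio was (0.25/0.75)/(0.30/0.70) = 0.778. A logit adjusted for procedure and ASA grade was fitted with and without country indicators, with 6,000 trials per scenario. The SAP does not give the following, so they are assumptions: 10 countries of unequal size, the procedure and ASA mix and effects, and the between-country SD of the log-odds.

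| SD | Power, country kept | Power, country dropped | Loss (points) | Type I error, kept | Type I error, dropped |
|---|---|---|---|---|---|
| 0.25 | 79.3% | 78.9% | 0.4 | 5.6% | 5.5% |
| 0.5 | 78.2% | 77.0% | 1.2 | 5.5% | 5.1% |
| 0.75 | 76.8% | 73.2% | 3.6 | 5.2% | 4.0% |
| 1.0 | 73.9% | 67.8% | 6.1 | 5.2% | 3.5% |

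The Monte Carlo standard error is 0.5 to 0.6 points for power and about 0.3 for type I error. With no country effect there was no difference.

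**Check of the mechanism at SD 1.0** (1,500 trials):

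- Null, country dropped: model SE 0.0878, empirical SD 0.0821, ratio 1.07. Implied type I error = 2Φ(−1.96 × 0.0878/0.0821) = 2Φ(−2.10) ≈ 3.6%.
- Null, country kept: 2Φ(−1.96 × 0.0959/0.0974) = 2Φ(−1.93) ≈ 5.4%.
- Alternative, country dropped: mean log odds ratio −0.2154, model SE 0.0900, empirical SD 0.0847. Power ≈ Φ[(0.2154 − 1.96 × 0.0900)/0.0847] = Φ(0.46) ≈ 67.7%.
- Alternative, country kept: Φ[(0.2553 − 1.96 × 0.0981)/0.0996] = Φ(0.63) ≈ 73.7%.

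These agree with the table.

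**Other runs under similar assumptions.**

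- Two further sets of 1,500 trials per scenario gave power losses of 0.7 and about 1 point at SD 0.3, 1.4 and about 2 at SD 0.6, and 4.1 and about 6.5 at SD 1.0. Type I error with country dropped at SD 1.0 was between 3.1% and 3.7%.
- Replacing a spline by a linear term cost under 0.5 points of power.
- Omitting a strongly prognostic age cost 2 to 2.5 points.
- The same 10-level factor was dropped with and without having been minimised (2,000 trials per scenario). At SD 0.5, power fell from 80.6% to 79.6% when minimised and from 81.2% to 79.3% when not. At SD 1.0 it fell from 75.7% to 69.8% and from 76.0% to 67.9%.

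**The case against.** **It takes two failures.** Step 1 keeps country, so step 2 needs the mixed model and then an ordinary logit to fail. This stands, and it limits the point mainly to the rarer outcomes.

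**Country is a sensible suspect.** As a fixed effect it uses one term fewer than the number of countries, some possibly sparse: 9 terms if there are 10 countries. Making three splines linear frees 3 terms and gender frees 1. A reader might infer that country is dropped for no reason. The SAP gives no reason, but this one is plausible.

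**The large losses need large country differences.** Around a 30% risk (log-odds −0.847), an SD of 1.0 puts 95% of countries between about 6% and 75% (−0.847 ± 1.96). An SD of 0.6 already spans about 12% to 58%. This stands: at moderate variation the loss is 1 to 2 points or less.

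**Power loss is not special to minimised factors.** A reader might infer that covariates outside the minimisation can be removed at almost no cost. The runs above show otherwise: the loss depends on how prognostic the covariate is, and it was at least as large when the factor had not been minimised. What is specific to the minimised factor is the conservative test, which creates no false positives.

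**The SAP has no single rule elsewhere.** Its acute kidney injury model drops gender and haemoglobin but keeps country, procedure and ASA grade. Its 24-hour cardiac model drops country and procedure but keeps age. Neither settles the right order here.

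**Conclusion.** The point holds in a narrow form. Step 2 gives up a design factor before a simplification that costs under 0.5 points of power. If step 2 is reached, the test becomes conservative and loses power: about 0.4 to 1 point at SD 0.25 to 0.3, 1 to 2 points at SD 0.5 to 0.6, and 4 to 7 points with type I error of 3% to 4% at SD 1.0. These figures rest on assumed country numbers, covariate mixes and between-country variation. They were computed at the primary outcome's event rate and not for kidney injury.

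Two stronger readings are not supported. The analysis does not stop reflecting the randomisation altogether, because procedure and ASA grade stay in the model at steps 2 and 3 and ASA grade is the last covariate removed. Nor is it an error that step 4 removes procedure before age, or that haemoglobin, creatinine and age outlast country. Procedure uses five terms and age one once linear, and any of these covariates may be strongly prognostic, so their order is a judgement. The SAP also gives no counts to show that a sparse procedure level, such as obesity surgery, would cause the failure.

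This is a minor point, unlikely to affect the primary result, but cheap to correct.

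**What to change.** Reorder the table and its example code:

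1. Country as a fixed effect (unchanged).
2. Make age, haemoglobin and creatinine linear where they are in the model, keeping country as a fixed effect.
3. Remove gender, still keeping country.
4. Remove country only if the model still fails.
5. Continue with the remaining removals in the SAP's existing order.

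The acute kidney injury model contains neither gender nor haemoglobin, so there only the age and creatinine splines change before country is removed.

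The cost is an edit to one table and a few lines of code, with no new data or patients. The downside is that, if sparse country terms are the real cause of failure, up to two more models are fitted before country goes, and spline flexibility and gender will have been given up as well. Pooling procedure levels, or placing haemoglobin, creatinine or age ahead of country or procedure, is not part of this change.

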#### **Interim analyses**

The data monitoring and ethics committee (DMEC) will review outcome data, safety data and recruitment data periodically during the trial. The DMEC will recommend that the trial be stopped early if:

- i) There is overwhelming evidence that is likely to convince a broad range of clinicians, including those supporting the trial and the general clinical community, that one trial arm is clearly indicated or contraindicated, and there was a reasonable expectation that this new evidence would materially influence patient management.
- ii) It becomes evident no clear outcome will be obtained.

No formal stopping rules are in place and no adjustments to the primary analysis will be made to account for any interim analysis performed for the DMEC. To maintain blinding, all unblinded analysis for the DMEC will be performed by an independent statistician who is not otherwise involved in the trial.

#### Subgroup analyses

A sub-group analysis will be performed for the primary outcome (postoperative infection within 30 days of randomisation) to assess whether the effect of the intervention differs by planned surgical procedure category. The sub-group analysis will be performed using the same analysis model as for the primary outcome, adding an interaction term between planned surgical procedure category and treatment arm. Planned surgical procedure category has six categories: i) resection of colon, rectum or small bowel; ii) resection of pancreas and bowel; iii) resection of stomach (non-obesity surgery); iv) resection of oesophagus (non-obesity surgery); v) obesity surgery; vi) other surgery involving gut resection.

The presence of an interaction will be tested using a likelihood ratio test comparing the sub-group analysis model, including the planned surgical procedure category by treatment interaction, and the primary analysis model, not including the interaction term. The test will be considered significant at the 5% level. All patients with complete outcome data will be included in the subgroup analysis. Within each surgical procedure category, we will report summary statistics of the outcome by treatment arm, and a treatment effects and 95% confidence intervals. A p-value for the interaction test will also be reported.

#### Sensitivity and secondary analyses

#### **Missing Data**

If the level of missing data for the primary outcome exceeds 1% of randomised patients, we will perform a sensitivity analysis to assess the robustness of our analysis of the primary outcome in regard to the data being missing-not-at-random (MNAR). For example, this could occur if patients who were discharged home and had no postoperative infection were less likely to respond to their telephone follow-up after 30 days than patients who did have a postoperative infection.

We define  $\delta_0$  and  $\delta_1$  as follows:

- ullet  $\delta_0$  = assumed event rate amongst patients with missing outcome data in the control arm
- $\delta_1$  = assumed event rate amongst patients with missing outcome data in the control arm

I.e. a value of  $\delta_0$ =0.3 indicates that we would assume 30% of patients with missing outcome data in the control arm experienced an event (postoperative infection).

We will conduct sensitivity analyses using the following values of  $\delta_0$ :

• 
$$\delta_0 = 0.15, 0.2, 0.25, 0.3, 0.35, 0.4$$

For each value of  $\delta_0$ , we will use the following values of  $\delta_1$ :

$$\delta_1$$
 =  $\delta_0$  + 0.1,  $\delta_0$  + 0.05,  $\delta_0$ ,  $\delta_0$  - 0.05,  $\delta_0$  - 0.1

For example, for the scenario where  $\delta_0$ =0.2 and  $\delta_1$ = $\delta_0$  + 0.1, we will assume that 20% of patients with missing outcome data in the control arm experience an event, and 30% of patients with missing data in the intervention arm experience an event.

For each different combination of  $\delta_0$  and  $\delta_1$  we will estimate a treatment effect and 95% CI using the imputation approach outlined below. For each scenario we will perform carry out 10 imputations and combine the results to give one estimate of the treatment effect for that scenario.

#### Imputation model

For each combination of  $\delta_0$  and  $\delta_1$  we will impute the missing data as follows. Patients with missing outcome data in the control arm will be randomly ordered within the dataset; the first  $\delta_0$  of patients will be set to experiencing an event, and the remaining 1- $\delta_0$  of patients will be set to not having experienced an event. The same approach will be used to impute missing data in the intervention arm.

#### Analysis model

We will analyse each imputed data set using the analysis model used to analyse the primary outcome (described in the section "Analysis of primary outcome").

#### Combining estimates from imputed datasets

We will combine estimates of the treatment effect and standard errors from the 10 imputed data sets on the log odds scale using Rubin's rules (7).

Details of Rubin's rules and example Stata code for this sensitivity analysis are given in appendix 4.

#### Mortality as a competing risk to postoperative infection

To assess the robustness of our primary analysis in regard to mortality acting as a competing risk for postoperative infection we will conduct a competing risk analysis for the primary outcome. Postoperative infection within 30 days of randomisation will be analysed using a competing-risk time-to-event model (6), which recognises mortality as a competing risk for postoperative infection. The model will adjust for the same baseline covariates as the primary analysis. Because there are no

facilities for analysing competing risk data using mixed effects models in Stata, we will use robust standard errors which account for clustering by country.

For each group we will present the median and interquartile range for time to first postoperative infection within 30 days of randomisation, the number (%) of patients who had postoperative infections within 30 days of randomisation, and the number (%) of patients who died before day 30 without having had a postoperative infection. Stata code for this analysis is given in Appendix 3.

#### Estimating the effect of the intervention for participants who undergo surgery

The main aim of the OPTIMISE II trial is to evaluate whether the intervention improves clinical outcomes compared to control in patients undergoing major elective surgery involving the gastro-intestinal tract. However, in rare instances, surgery may be delayed or cancelled, and so the patient may not undergo surgery before the outcome is collected.

We will therefore conduct a secondary analysis to estimate the effect of the intervention in patients undergo surgery within the follow-up period. This analysis will be conducted for the primary outcome (postoperative infection within 30 days of randomisation), acute cardiac events within 24 hours and 30 days of randomisation.

We will use the method proposed by Bond and White (8) to estimate the effect of the intervention in patients who received surgery. Treatment effects are estimated using a Bayesian method combined with an instrumental variables approach. Full details are provided in the following reference (8). Briefly, this approach involves specifying an informative prior for the effect of receiving the control intervention compared with receiving no surgery. Uninformative priors are used for all other parameters in the model. The approach can provide valid estimates of the effect of intervention in patients who undergo surgery when the prior for the effect of the control intervention vs no surgery is correctly specified.

In this analysis, we will consider patients who do not undergo surgery within the follow up period for the respective outcome as having not undergone surgery. For the outcomes measured at 30 days (postoperative infection within 30 days, acute cardiac event within 30 days), we will count any patient whose date of surgery is 31 days or more after randomisation as not having received surgery. For acute cardiac event within 24 hours of randomisation we will count anyone whose date of surgery is 2 days or more after the date of randomisation as not having received surgery. Patients for whom the date of surgery is missing will be excluded from the analysis (as will patients with missing outcome data).

Our analysis will be based on a difference in proportions between groups; we opted not to use an odds ratio as our effect measure of interest, as we expected the event rate in the no surgery group to be close to zero for some outcomes, which could lead to difficulties when estimating an odds ratio.

Due to concerns around convergence with small event rates or a low proportion of patients not undergoing surgery, these secondary analyses will not adjust for covariates. In addition, if the event rate across all patients is less than 5% for any outcome, we will not conduct the analysis on this outcome.

The analysis will be conducted using Stata 15. Statistical code to implement the analysis is available in appendix 3.

In order to allow comparison with the intention to treat estimate, we will conduct an additional ITT analysis for each of the outcomes under consideration (postoperative complications within 30 days, acute cardiac events within 24 hours and 30 days) based on a difference in proportions between treatment groups, unadjusted for covariates. This will be based on a generalised linear model with binomial family and identity link.

Our priors will be based on a normal distribution, with means and variances given in Table A for the effect of the control vs no surgery. To assess the sensitivity of our results to choice of prior we will perform two additional analyses using different priors. Main priors are based on the event rates for the subset of patients in the OPTIMISE I trial who were in the control arm and eligible for OPTIMISE II. We will use the default Stata priors for other parameters in the model. All analyses will be conducted using seed 1234 for the random number generator, with 2500 MCMC burn in, and a 100,000 MCMC sample size (102,500 total MCMC iterations).

Table A – Parameters for priors for effect of usual care vs no surgery

| Outcome                          | Prior                    | Mean a | Standard deviation b |
|----------------------------------|--------------------------|-------------------|---------------------------------|
| Postoperative infection          | Main                     | 0.31              | 0.027                           |
| within 30 days of                | Sensitivity 1 (lower)    | 0.28              | 0.027                           |
| randomisation (primary outcome)  | Sensitivity 2 (higher)   | 0.34              | 0.027                           |
| Acute cardiac event              | Main                     | 0.15              | 0.021                           |
| within 30 days of                | Sensitivity 1 (lower)    | 0.12              | 0.021                           |
| randomisation                    | Sensitivity 2 (higher)   | 0.18              | 0.021                           |
| Acute cardiac event              | Main                     | 0                 | 0.01                            |
| within 24 hours of randomisation | Sensitivity 1 (higher 1) | 0.01              | 0.01                            |
|                                  | Sensitivity 2 (higher 2) | 0.02              | 0.01                            |

<sup>a This represents the difference in proportions between patients receiving control vs. having no surgery

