# Secondary analysis - estimating the effect of the intervention for participants who undergo surgery (Stata 15)

```
/*Compliance variables required:
c z1: binary indicator equal to 1 if patient is in intervention group and
underwent surgery during the time-frame of the specified outcome, 0 otherwise (and
missing if date of surgery is missing)
c z0 binary indicator equal to 1 if patient is in usual care group and underwent
surgery during the time-frame of the specified outcome, 0 otherwise (and missing if
date of surgery is missing)
reg c z1 treat
predict prob new trt
reg c z0 treat
predict prob std trt
Note in the following command the option "nomleinitial" is required to stop Stata
using a maximum likelihood estimate for initial values. This is not possible due to
the collinearity of the variables in the model. The option "collinear" is required
to supress collinearity check.
*/
bayes, prior ({postopinfec 30: prob std trt}, normal(0.31, 0.27)) ///
             nomleinitial rseed(1234) mcmcsize(100000): ///
             binreq postopinfec 30 prob new trt prob std trt, rd collinear
bayesstats summary ({postopinfec 30:prob new trt} ///
      - {postopinfec 30:prob std trt})
bayesgraph diagnostic {postopinfec 30: prob std trt} {postopinfec 30: prob new trt}
```

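### The surgery-only analysis counts non-operated patients as having had no surgery, but its missing-date rule would exclude those whose operation was cancelled, and its code follows neither rule

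*SAP*

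**What the plan says.** SAP section 5, under the heading on participants who undergo surgery, gives the reason for the analysis: "in rare instances, surgery may be delayed or cancelled, and so the patient may not undergo surgery before the outcome is collected". The general rule follows: "we will consider patients who do not undergo surgery within the follow up period for the respective outcome as having not undergone surgery".

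Three working rules put this into practice, all based on the operation date:

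- 30-day outcomes: "we will count any patient whose date of surgery is 31 days or more after randomisation as not having received surgery".
- 24-hour outcome: "we will count anyone whose date of surgery is 2 days or more after the date of randomisation as not having received surgery".
- No date: "Patients for whom the date of surgery is missing will be excluded from the analysis (as will patients with missing outcome data").

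Appendix 3 defines the indicators `c_z1` and `c_z0` as 1 for surgery inside the outcome window in the relevant arm and 0 for everyone else, but "missing if date of surgery is missing". Each indicator is regressed on allocation, `predict` supplies fitted proportions, and a Bayesian `binreg` model relates the outcome to those proportions. Neither `predict` nor `binreg` carries a sample restriction.

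**The concern.** An operation that never took place would ordinarily have no date. The SAP names no item that separates a patient who was never operated on from one who was operated on with the date left unrecorded. Under the date rule and the Appendix 3 coding both are missing. The general rule would keep the first patient as no surgery; the date rule removes that patient. Cancelled patients are one of the two groups named as the reason for the analysis.

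Two things are at stake. First, dropping these patients selects on something that happens after randomisation in an open trial, which the instrumental-variable approach is meant to avoid, and it leaves the prior sensitivity analyses little to work on. Second, the code performs a third analysis that matches neither rule. `reg` omits patients with a missing indicator, but unrestricted `predict` then gives each of them a value from allocation alone, so they enter the outcome model without having counted in the surgery proportion.

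**Working it through.** **Inputs.** From SAP section 4: 30% risk with usual care, 25% with the intervention, 1251 per arm. From Table A: prior means 0.28, 0.31 and 0.34 for usual care versus no surgery. The SAP gives no share of non-operated patients and speaks only of "a low proportion of patients not undergoing surgery". I therefore assume cancelled shares `c` of 1% to 5% and shares `d` of 0% to 0.5% delayed past day 30. I also assume no infections without surgery, and cancellation unrelated to risk. The true effect in operated patients is then −0.0500.

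**The plan's own figure.** With pooled variance, two-sided 5% and 80% power, n = [1.960·√(2·0.275·0.725) + 0.842·√(0.30·0.70 + 0.25·0.75)]² / 0.05² = 1250.7. This rounds up to 1251 per arm, so the stated size reproduces and the two risks are a fair base.

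**Formula.** Let E1 and E0 be the mean outcomes and q1 and q0 the fitted surgery proportions (intervention, usual care). Holding the usual-care effect at its prior mean m, the Appendix 3 model implies

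D = (E1 − E0)/q1 + m·(q0 − q1)/q1.

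**Three codings.**

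- A, cancelled coded 0: q = 1 − c − d, E = risk × (1 − c − d).
- B, the text's exclusion: q = (1 − c − d)/(1 − c), E = risk × q.
- C, the code as printed: q from B, E from A.

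| Assumed shares | ITT | A | B | C |
|---|---|---|---|---|
| 1% cancelled, 0.5% delayed, both arms | −0.0493 | −0.0500 | −0.0500 | −0.0495 |
| 4% cancelled, none delayed, both arms | −0.0480 | −0.0500 | −0.0500 | −0.0480 |
| 5% cancelled, none delayed, both arms | −0.0475 | −0.0500 | −0.0500 | −0.0475 |
| 4% v 2% cancelled, 0.5% delayed each | −0.0538 | −0.0504, −0.0498, −0.0492 | −0.0500 for all m | −0.0540 for all m |

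Three values in a cell are for m = 0.28, 0.31 and 0.34. Row two, coding C: E1 = 0.96 × 0.25 = 0.240, E0 = 0.96 × 0.30 = 0.288 and q1 = q0 = 1, so D = −0.048. Row four, coding C, m = 0.31: E1 = 0.955 × 0.25 = 0.23875, E0 = 0.975 × 0.30 = 0.2925, q1 = 0.955/0.96 = 0.99479 and q0 = 0.975/0.98 = 0.99490, so D = −0.05375/0.99479 + 0.31 × 0.000107 = −0.0540.

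**Patients lost under B.** 1% of 2502 is about 25 and 5% is about 125. In row one the no-surgery share the model sees falls from 1.5% to about 0.5%. In row three it falls from 5% to 0%; the fitted proportions then equal the allocation indicators and the prior cannot move the difference.

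**Prior sensitivity.** The multiplier on m is (q0 − q1)/q1. In row four it is 0.020/0.955 = 0.0209 under A but 0.000107 under B. Over the 0.06 spread in prior means, the estimate moves by 0.0013 under A and by less than 0.00001 under B. With equal shares in both arms the multiplier is 0 under every coding, so this loss arises only when cancellation differs by arm.

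**The case against.** The strongest reply is that the general rule already covers cancelled operations and that the 31-day and 2-day rules only classify operations that have a date. On that reading a date that does not apply is not a missing date, and the exclusion concerns only dates that were not recorded. Appendix 3 fits this in part, since 0 is its default. This is probably what was meant. But the exclusion and the code comment make no exception for operations that never happened, and a programmer following them literally would drop those patients. That the date is blank after a cancellation remains an inference.

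On the code, one can say that the appendix leaves out data preparation generally: the planned mean imputation of covariates is not in the primary-outcome code either. A missing restriction therefore does not prove that the exclusion would be skipped. That is fair, but as printed the code and the text define different analyses.

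Size also favours the plan. The 0.2-point gap compares with a standard error of about √(0.3975/1251) = 1.8 points. The text's exclusion, taken alone, differs from correct coding by less than 0.001 in every row above.

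A reader might infer that the exclusion manufactures a benefit. Suppose 3% more intervention patients are cancelled, with a 50% infection risk had they been operated on. The intervention risk then falls to (0.25 − 0.03 × 0.5)/0.97 = 24.2%, a spurious 0.8 points. That figure does not support this point, because correct coding does not remove it. Keeping those patients as no surgery gives −0.065/0.97 + m × 0.03/0.97 = −5.83, −5.74 and −5.65 points for the three prior means, against −5.77 with exclusion and an assumed truth of −5.0. Nor does anything in the SAP suggest such selective cancellation: randomisation takes place shortly before surgery, and non-surgery is expected to be rare.

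**Conclusion.** The point holds as an internal inconsistency in a secondary analysis. The general rule, the missing-date rule and the printed code treat a patient with no operation date in three different ways. If cancelled operations have no date, the text drops the cancelled patients and keeps only those with a late date, and the prior sensitivity analyses lose nearly all their content when cancellation differs between arms. The code instead returns roughly the ITT difference: 4.8 rather than 5.0 points at an assumed 4% cancelled per arm, and about 5.4 at 4% versus 2% cancelled with 0.5% delayed. The shift can therefore go either way.

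These sizes rest on assumed cancellation shares, no infections without surgery, and cancellation unrelated to risk. A reader might conclude that every patient the analysis was meant for is lost, or that the main result is in doubt. Neither follows: delayed patients with a recorded late date stay in, and the primary ITT analysis does not use the operation date. This is worth correcting before the analysis is run, but it does not threaten the trial's main conclusion.

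**What to change.** In SAP section 5 and Appendix 3, define `c_z1` and `c_z0` from surgery status:

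- 1 in the relevant arm if surgery took place inside the outcome window;
- 0 if surgery was cancelled, never done, or done after the window;
- missing only if it is unknown whether surgery took place, or if it took place on an unknown date.

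Fit both `reg` commands and `binreg` to the same patients, namely those with surgery status and outcome known. Add to Table 7, by arm, the numbers cancelled or never done, done late, and excluded as unknown.

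The cost is a few sentences, a sample restriction in the code and extra columns in one table. It needs an item recording whether surgery took place. Table 2 plans a row for the procedure performed, which suggests that the information is collected, but the SAP does not confirm a cancellation indicator, so the sponsor should check the case report form.
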